9.3. Analysis of Other Efficacy Data

These other efficacy data comprise efficacy outcomes of interest that are not strictly captured as primary, secondary, or exploratory outcomes measures of efficacy. This includes the patient global impression score. Note, the exploratory outcome measure of presence/absence of COVID-19 symptoms at Day 60 is included in [Section 11.3](#).

These other efficacy data will be presented for the FAS.

Analysis of the patient global impression questionnaire will be presented by treatment group. This form was revised part way through the trial in protocol version 3 and went from one question to three. All available data will be analyzed and the responses in the final analysis will include the questions asked on the first version of the questionnaire as well as the second. Any participants who were enrolled prior to the time when their site implemented protocol version 3 will be summarized as missing for questions 1 and 3 on the second version of the questionnaire for the relevant timepoints and excluded from any time to event analysis for those questions. Answers to the single question on the first version of the questionnaire will be combined with answers to the second question on the second version of the questionnaire.

Median time to return to usual health, median time to return to usual activities, and median time to no COVID-19-related symptoms will be summarized for each treatment group using Kaplan-Meier methods. Responses on days 7, 14 and 28 will also be summarized using shift tables from baseline. The proportion of patients who return to usual health, return to usual activities, and with no COVID-19-related symptoms will be tabulated by Days 7, 14, 28, and 60; a Chi-square or Fisher's exact test will compare the treatment arms for each question at each timepoint.

If patients are missing the patient global impression questions at all timepoints, then for time to event analyses, they will be censored (not returned to usual health, activities and/or symptoms not resolved) at Day 60 or at date of study discontinuation, if earlier than Day 60.

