4. GENERAL ANALYTIC CONSIDERATIONS

4.1. Study Size and Power

A total of approximately 500 patients will be randomized using a 1:1 assignment ratio. The sample size is selected to achieve at least 80% power to detect a difference at the 0.05 level of significance (2-sided) in the proportion of patients who experience any emergency room visit or hospitalization, or death over 28 days.

This sample size is based on an assumed 3% event rate for the sargramostim arm and a 10% rate for the placebo arm (risk ratio of 0.30) in unvaccinated patients (similar to that observed for bamlanivimab BLAZE-1 study [Chen, 2021; Gottlieb, 2021; US FDA, 2021]). As discussed in protocol Section 4.6, the rate of any emergency room visits or hospitalization, or death over 28 days is expected to be very low, or near zero for vaccinated patients.

It is also assumed that the proportion of vaccinated patients will be approximately 20-25% of the study population, with enrollment of patients who have completed a COVID-19 vaccination regimen or participated in a COVID-19 vaccine clinical trial capped at approximately 100 patients; no events are expected to occur in these patients for either treatment arm. Therefore, the overall event rate (for unvaccinated and vaccinated patients combined) for the primary endpoint is expected to be 2.4% for sargramostim and 8.0% for placebo (risk ratio of 0.30) and maintains at least 80% power.

Note that completion of a COVID-19 vaccination regimen or participation in a COVID-19 vaccine clinical trial (yes, no) is one of the randomization stratification factors (protocol Section 6.2).

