4.3. Test Size, Confidence Levels, and Precision

Unless otherwise noted, reported confidence intervals will all be computed at the 95% confidence level; p-values will be assessed at the two-sided 0.05 significance level. Unless otherwise specified below, continuous variables will be summarized using number of patients, mean, standard deviation, median, minimum, maximum, and 25th and 75th percentiles as appropriate. Categorical variables will be summarized using number and percentage of patients in each category. The number of patients with missing responses (or variables) will be tabulated.

As this is a Phase 2b study, no adjustments for multiple comparisons will be made.

Unless otherwise specified, the following guidelines will be followed when displaying statistics:

- measures of central tendency and percentiles will be displayed with one decimal place more than the raw (collected) data,
- measures of variability will be displayed with two decimal places more than the raw (collected) data,
- percentages will be displayed with one decimal place, and
- p-values will be displayed to 4 decimal places and any less than 0.0001 will be displayed as “<0.0001”.

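### Section 9.3 summarizes three times to recovery by Kaplan-Meier but plans no comparison of the curves, leaving four unadjusted fixed-day tests per question and no single answer

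*SAP*

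**What the plan says.** Section 9.3 covers the patient global impression questionnaire. The median times to the three recovery outcomes "will be summarized for each treatment group using Kaplan-Meier methods". The proportions recovered are shown at four days (7, 14, 28 and 60). For the comparison, the plan gives either a Chi-square test or Fisher's "exact test will compare the treatment arms for each question at each timepoint". Nothing else in 9.3 compares the arms. It names no log-rank test, Cox model or hazard ratio, and no interval for a difference.

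Section 4.3 sets the error rate: "p-values will be assessed at the two-sided 0.05 significance level", and "no adjustments for multiple comparisons will be made".

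Section 9.2.2 handles the same type of data differently. Time to progression gets Kaplan-Meier estimates, a log-rank test stratified by the two randomization factors as appropriate, a Cox hazard ratio with 95% CI, and a check of proportional hazards.

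Two further statements in 9.3 bear on the point. Participants enrolled before their site implemented protocol version 3 are left out of the time-to-event analyses of questions 1 and 3. The censoring rule is written for the time-to-event analyses only, and only for patients with no questionnaire response at any timepoint.

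**The concern.** The plan sets up three time-to-event variables and then does not compare them as such. Each arm gets a median. The p-values come from proportions on four days, and no day is designated as the main one. If the arms differ on Day 14 but not on Days 7, 28 or 60, the plan does not say what has been shown about speed of recovery.

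Two things are at stake. With four unadjusted looks per question, a chance difference on one day is more likely than the nominal 5% suggests. And nothing estimates the overall difference in recovery time with its uncertainty. A log-rank test chosen after unblinding would be post hoc. The SAP gives no reason for treating 9.3 differently from 9.2.2.

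**Working it through.** **Inputs.** From the SAP: "A total of approximately 500 patients will be randomized using a 1:1 assignment ratio" (section 4.1), so about 250 per arm; two-sided 0.05 (4.3); Days 7, 14, 28 and 60 (9.3). Not in the SAP and therefore assumed: the control median time to recovery, the hazard ratio (HR), exponential times and, in the simulations, 8% to 10% dropout and daily assessment.

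**1. The plan's own power figure.** The only one concerns the primary endpoint: "at least 80% power to detect a difference at the 0.05 level of significance (2-sided"). The overall event rate "is expected to be 2.4% for sargramostim and 8.0% for placebo (risk ratio of 0.30) and maintains at least 80% power". For two proportions, power = Φ[(|p1 − p2| − 1.96·SE0)/SE1].
- SE0 = √(2 × 0.052 × 0.948/250) = 0.01986
- SE1 = √((0.024 × 0.976 + 0.080 × 0.920)/250) = 0.01970
- (0.056 − 0.0389)/0.01970 = 0.867, so power is 80.7%

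The figure reproduces. The same formula is used below. The SAP states no power for the 9.3 outcomes.

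**2. False positives.** There are 3 questions × 4 days = 12 tests. If they were independent, the chance of at least one false positive would be 1 − 0.95⁴ = 18.5% per question and 1 − 0.95¹² = 46.0% over all twelve. These are upper guides, because the tests reuse the same patients and are correlated. Simulation with no effect (250 per arm, 10% dropout, daily assessment to Day 28 and then Day 60, 2,000 trials) gave 14.6% per question at a median of 14 days and 15.4% at 10 days. The log-rank test gave 4.9% in both. Runs with 8% dropout gave about 14% to 17%.

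**3. Power with a constant HR.** Log-rank power = Φ[ln(HR)·√(d/4) − 1.96], where d is the number of recoveries by Day 60. For a control median of 14 days and HR 1.3:
- The proportions recovered by Day 60 are 0.949 and 0.979, so d = 250 × (0.949 + 0.979) = 482
- 0.2624 × √120.5 − 1.96 = 0.92, so power is 82.1%
- On Day 28 the proportions are 0.750 and 0.835. Then (0.0851 − 1.96 × 0.03627)/0.03607 = 0.387, so power is 65.1%

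Power (%) at HR 1.3, 250 per arm, no dropout:

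| Control median (days) | Log-rank | Day 7 | Day 14 | Day 28 | Day 60 |
|---|---|---|---|---|---|
| 7 | 83.4 | 55.9 | 65.1 | 47.9 | 9.1 |
| 10 | 83.1 | 47.0 | 62.4 | 61.4 | 23.8 |
| 14 | 82.1 | 38.3 | 55.9 | 65.1 | 44.1 |
| 21 | 79.2 | 28.9 | 45.7 | 61.6 | 60.9 |
| 28 | 75.4 | 23.5 | 38.3 | 55.9 | 64.9 |

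Over these medians and HRs of 1.2 to 1.4, the log-rank test gains 7.5 to 20.7 points over the best single day.

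**4. The four tests taken together.** At HR 1.3 with 10% dropout and medians of 10, 14 and 21 days, at least one of the four tests is significant in 80.3%, 81.2% and 81.5% of trials. The log-rank test is significant in 79.2%, 78.1% and 75.9%. The set of tests detects an effect about as often, at roughly three times the error rate shown in step 2.

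**5. A short-lived effect** (simulated, 8% dropout):
- HR 1.5 to Day 7 and 1.0 after, median 10 days: log-rank 54%, Day 7 test 85%
- The same effect, median 14 days: 37% against 74%
- HR 1.4 to Day 14 and 1.0 after, median 10 days: log-rank 76%, Day 14 test 83%

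**6. Sample size.** Because of the version 3 exclusion, 250 per arm is an upper bound for questions 1 and 3. At an assumed 175 per arm (median 10 days, HR 1.25), log-rank power is about 55%, against 66% to 72% in simulations at 250 per arm.

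**The case against.** The strongest objection is that these outcomes sit below the primary, secondary and exploratory measures. Medians with fixed-day tables are a legitimate choice at that level, and sections 9.1 and 9.2.1 use the same day-by-day format. Section 4.3 openly accepts unadjusted comparisons. That stands and sets the priority low. It does not explain why a time-to-event outcome with planned p-values has no comparison of the curves. In 9.1 and 9.2.1 the day-by-day tests accompany a modeled effect estimate with a confidence interval.

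It could also be said that the plan covers timing elsewhere. The medians are reported, symptom scores are tested over time by a repeated-measures model in 9.2.3, and sections 12.1 and 12.2 allow Cox models and other methods. But 9.2.3 concerns a different questionnaire, and section 12 is optional and fixes nothing for 9.3.

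A reader might infer more than the document supports:
- **That a real effect is likely to be missed.** Step 4 shows otherwise. Under a constant hazard ratio, the four tests together find an effect about as often as the log-rank test. The cost is in false positives and in the lack of one answer.
- **That the log-rank test is always stronger.** Treatment lasts 5 days, so an early effect is plausible, and step 5 shows the ranking reversing. Because the SAP designates no single day, that advantage is open only to someone who picks the day after seeing the data.
- **That patients censored early count as not recovered in the proportions.** Section 9.3 does not say how they enter.

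The questionnaire schedule is left to the protocol. If responses came only on Days 7, 14, 28 and 60, simulated log-rank power would be 64% (median 10 days, HR 1.25), 66% (14 days, 1.25) and 76% (10 days, 1.30). The best single day with daily assessment reaches 47% to 49%, 51% to 52% and 61% to 63% in those settings.

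**Conclusion.** The point holds as a minor one. Section 9.3 names no comparison of the three recovery curves and no effect estimate with an interval, and leaves four unadjusted answers per question. The main harm is the lack of a single prespecified answer, with a false-positive chance of about 14% to 17% per question under the simulated settings. The power gain of about 8 to 21 points over the best single day depends on a constant hazard ratio, exponential recovery and 250 per arm, none of which the SAP states for these outcomes. It can reverse if the effect is short-lived. Absolute power for questions 1 and 3 will be lower than shown if a material number of patients enrolled before version 3.

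**What to change.** In section 9.3, add for each of the three outcomes a log-rank test and a Cox hazard ratio with 95% CI. Stratify by the randomization factors as appropriate, include the proportional-hazards check as in 9.2.2, and use the same patients as the Kaplan-Meier analysis. Name this as the main between-arm comparison for each question. Keep the Day 7, 14, 28 and 60 proportions as supportive; whether their tests are also kept is a matter of preference.

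The cost is a few sentences in the SAP before unblinding and reuse of the 9.2.2 method on time-to-event data that 9.3 already requires. The downside is small: less power than an early fixed-day test if the effect is short-lived, and a hazard ratio that must be read with the proportional-hazards caveat.

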10. ASSESSMENT OF SAFETY (SECONDARY OUTCOME MEASURES)

All safety analyses will be performed using the Safety Population. All hospitalizations, emergency room visits, and deaths will be considered in the efficacy rather than safety analyses for this study. All patients will be assessed regularly for potential adverse events (AEs) occurring from the time the patient provides informed consent until participation in the study has ended (up to 60 days after the first dose of study medication); see Protocol Section 10 for Adverse Event definitions for this study. All AEs reported in the study database will be included in summaries, regardless of whether they are determined to be associated with COVID-19.

Other safety analyses will summarize treatment administration and exposure, laboratory parameters, vital signs, and pulse oximetry (oxygen saturation).

No missing data will be imputed for safety analysis nor will formal hypothesis testing be performed.

Treatment-emergent AEs (TEAEs) will include AEs which newly emerge on or after the first study drug dosing or a preexisting medical condition judged by the Investigator to have worsened in severity or frequency or changed in character on or after the first study drug dosing.

A treatment-related AE is defined as an AE which is considered to have a possible, probable, or definite relationship to the study drug. A device-related AE is defined as an AE which is considered to have a possible, probable, or definite relationship to the nebulizer. AEs will be graded according to the National Cancer Institute's Common Terminology Criteria for Adverse Events (NCI CTCAE).

Patient level listings of AEs, serious AEs (SAEs), study treatment duration and exposure, laboratory parameters (including abnormal flags), vital signs, pulse oximetry and physical examination will be provided for all available assessments. Each listing will include patient ID, treatment arm, randomization strata, age, race, and sex. Any partial or missing dates will be reported as recorded in study data on patient listings.

Patient profiles may be generated for patients with SAEs, ER visits, hospitalizations, early discontinuation from treatment, and deaths. These patient profiles will include demographics and study treatment data, along with key laboratory data, concomitant medications, medical history, and adverse event data. Additional profiles may be generated for any identified suspected unexpected serious adverse reactions.

10.1. Summary of Study Treatment Duration and Exposure

All administered doses will be listed and summarized descriptively for each treatment day and treatment arm. Duration of study treatment for each patient will be summarized, with duration defined as the number of days on which the patient received treatment, up to a total of five. The number and percentage of patients per treatment arm that complete all 5 planned doses will be tabulated.

10.2. Analysis of Secondary Safety Endpoint

A secondary trial objective is to evaluate safety of inhaled sargramostim in patients with COVID-19 using adverse events (AEs) up to Day 60. Numbers and percentages of patients experiencing AEs will be presented by treatment arm.

An overview of the number of events and number and percentage of patients with AEs, SAEs, TEAEs, TEAEs related to study treatment or device, TEAEs related to COVID-19, serious TEAEs, fatal TEAEs, TEAEs that led to treatment discontinuation, and TEAEs by severity will be tabulated by treatment arm and overall.

TEAEs will be summarized as follows, by MedDRA system organ class (SOC) and preferred term (PT) and overall:

- All TEAEs
- All TEAEs by study period (dosing/post-dosing)
- All TEAEs by maximum severity (CTCAE toxicity grade)
- All treatment-related TEAEs by maximum severity (CTCAE toxicity grade)
- All device-related TEAEs by maximum severity (CTCAE toxicity grade)
- Serious TEAEs
- Treatment-related serious TEAEs
- Fatal TEAEs (CTCAE Grade 5 and/or an outcome of fatal)
- TEAEs leading to discontinuation of treatment

If a patient experiences multiple AEs under the same PT (SOC), then the patient will be counted only once for that PT (SOC). If a patient experiences the same AE more than once with different toxicity grade, the event with the highest grade will be tabulated in “by maximum severity” tables.

10.3. Analysis of Additional Safety Data

Safety laboratory parameters will include hematology and chemistry parameters collected at baseline, Day 14 and Day 28. Hematology parameters will include complete blood count with differential, hemoglobin, hematocrit, and absolute counts for white blood cells, platelets, neutrophils, lymphocytes, eosinophils, and monocytes. Chemistry parameters will include albumin, blood urea nitrogen, creatinine, alanine aminotransferase, aspartate aminotransferase, lactate dehydrogenase, alkaline phosphatase, direct and total bilirubin, glucose, total protein, sodium, potassium, chloride, bicarbonate, calcium, and uric acid. Additional safety laboratory parameters will include serum ferritin, CRP, and d-Dimer (planned analyses for these parameters are included in [Section 11](#)). Vital sign assessments will include temperature, blood pressure, pulse rate, and respiration rate. Pulse oximetry will also be summarized. Results for pulse oximetry may be influenced by altitude of clinical sites, so a subgroup analysis of patients enrolled at high altitude sites may be warranted (if there are sufficient numbers of patients).

Laboratory parameters, vital signs, and oxygen saturation (pulse oximetry) and change from baseline at each time point will be presented using summary statistics (n, mean, standard deviation [SD], median, interquartile range, minimum, and maximum values) by treatment group. Abnormal laboratory findings, will also be tabulated using percentages for below and above the normal range. No inferential testing will be performed to compare the differences between the treatment groups.

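### The only by-arm laboratory abnormality table counts values below and above the normal range, so it neither separates new or worsened abnormalities from those present at entry nor shows their severity

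*SAP*

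**What the plan says.** SAP Section 10.3 sets the sampling for these parameters: "Safety laboratory parameters will include hematology and chemistry parameters collected at baseline, Day 14 and Day 28". It then plans two by-arm outputs. The first is continuous: values and "change from baseline at each time point will be presented using summary statistics", including minimum and maximum. The second is categorical: "Abnormal laboratory findings, will also be tabulated using percentages for below and above the normal range". The section closes by keeping all of this descriptive: "No inferential testing will be performed to compare the differences between the treatment groups".

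Three other places bear on the point.
- Section 10 plans patient-level listings of "laboratory parameters (including abnormal flags), vital signs, pulse oximetry and physical examination will be provided for all available assessments".
- Section 10 also states that "AEs will be graded according to the National Cancer Institute's Common Terminology Criteria for Adverse Events (NCI CTCAE"). It defines treatment-emergent events relative to the patient's condition before the first dose, and Section 10.2 tabulates them by maximum grade. That grading is stated for adverse events, not for laboratory values.
- Section 9.3 uses baseline-referenced tables for the global impression questionnaire: "Responses on days 7, 14 and 28 will also be summarized using shift tables from baseline". No such table is planned for laboratory data.

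**The concern.** Section 3 enrols patients who are symptomatic with COVID-19, so abnormal values before the first dose are plausible. A later percentage out of range then mixes two groups: patients who were already out of range in that direction and remain so, and patients who became abnormal on study. Only the second group is informative about a new effect of treatment. A patient who was already high at baseline and rises much further falls in the same cell before and after, so worsening does not register at all. A value just past the limit and an extreme one also carry equal weight.

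At stake is how easily a reader of the study report can see an imbalance in new or severe laboratory abnormalities. These data support the secondary safety objective, although the secondary safety endpoint itself is adverse events up to Day 60.

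**Working it through.** **1. Text check.** The SAP states no figure on this point, so there is nothing of its own to reproduce. The laboratory outputs compare as follows.

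| Output | By arm | Referenced to baseline | Severity | Patients per arm with a new or high-grade abnormality |
|---|---|---|---|---|
| Percent below/above range (10.3) | yes | no | no | no |
| Values and change from baseline (10.3) | yes | yes | minimum and maximum only | no |
| Listings with abnormal flags (10) | arm shown per patient, not summarised | no | no grade stated | no |
| Treatment-emergent adverse events by grade (10, 10.2) | yes | yes | yes | only for abnormalities reported as adverse events |

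**2. Algebra of the dilution.** For one parameter and one direction, let b be the share out of range at baseline, q the share of those still out of range later, and r the rate of new abnormality among patients normal at baseline. I take the percentage to be of patients at a visit, and b and q to be equal in the two arms. Then:

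- planned table: b·q + (1 − b)·r
- difference between arms in the planned table: (1 − b)·(r1 − r0)
- excess patients, planned table, n per arm: n·(1 − b)·(r1 − r0)
- excess patients, new-onset table, n·(1 − b) normal at baseline: also n·(1 − b)·(r1 − r0)

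The ratio shrinks because b·q is added to both arms. The absolute excess does not change.

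**3. Numbers.** About 500 patients at 1:1 (Section 4.1) gives 250 per arm. All rates below are assumed.

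New abnormality in 10% versus 5%, a true ratio of 2.0:

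| b | q | Planned table | Ratio | Excess patients (both tables) |
|---|---|---|---|---|
| 10% | 30% | 12.0% vs 7.5% | 1.60 | 250 × 0.045 = 225 × 0.05 = 11.25 |
| 30% | 50% | 22.0% vs 18.5% | 1.19 | 250 × 0.035 = 175 × 0.05 = 8.75 |
| 50% | 80% | 45.0% vs 42.5% | 1.06 | 250 × 0.025 = 125 × 0.05 = 6.25 |

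A second case has b = 30%, q = 50%, and new abnormality in 12% versus 5%:

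- Planned: 0.15 + 0.70 × 0.12 = 23.4% versus 0.15 + 0.70 × 0.05 = 18.5%, ratio 1.26. The difference is 4.9 points with standard error √[(0.234 × 0.766 + 0.185 × 0.815)/250] = 3.6 points, so 1.35 standard errors.
- New-onset, 175 normal at baseline per arm: 12% versus 5%, ratio 2.4. The difference is 7 points with standard error √[(0.12 × 0.88 + 0.05 × 0.95)/175] = 3.0 points, so 2.37 standard errors.
- Excess in both: 250 × 0.049 = 175 × 0.07 = 12.25 patients.

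The standard-error multiples describe how far the difference stands out from noise. They are not a proposed test.

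**4. Severity.** No calculation is needed. A single cell above the limit and a single cell below it cannot distinguish degrees, and a patient who worsens within a cell adds nothing to the difference between arms.

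**The case against.** A reader might infer that the SAP gives laboratory data no link to baseline and that severe values would go unseen. The document does not support this. Change from baseline is planned by arm at each visit, minima and maxima are shown, listings carry flags and treatment arm, and a laboratory abnormality reported as an adverse event is assessed against pre-dose status and graded. What remains is narrower. Means and medians can mask a few large individual shifts, a minimum or maximum shows one value, listings are not a comparison, and the adverse event route depends on what is reported as an event.

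A reader might also infer that the table conceals a treatment excess. Step 2 shows that it does not for new abnormalities: the same number of excess patients appears in both tables. Dilution also requires the baseline and new abnormalities to lie in the same direction, because low and high are tabulated separately. Equal recovery from the illness in both arms cancels in the comparison with placebo, so recovery offsets toxicity only if the arms recover differently, and nothing in the SAP establishes that.

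Two further objections have some force. With only Days 14 and 28 scheduled after baseline, a worst-value summary adds little beyond the by-visit tables unless unscheduled samples are common. Table shells are held separately (Section 14) and might include shift tables, but the SAP text does not require them. Nor is the use of shift tables for a questionnaire an inconsistency; it only shows that the format is already in use.

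**Conclusion.** The point holds as a weakness of one descriptive table. Section 10.3 specifies a laboratory abnormality display that mixes entry abnormalities with new or worsened ones in the same direction and ignores severity, and no other planned output counts patients per arm with new or high-grade values.

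The severity part rests on no assumption. The dilution part depends on rates that the SAP does not give. Over assumed baseline abnormality of 10% to 50% and persistence of 30% to 80%, the three combinations tabulated show a true ratio of 2.0 as 1.60, 1.19 and 1.06, with the absolute excess unchanged. Because no laboratory testing is planned and none is proposed, probabilities of reaching significance are not a fitting measure of the loss.

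The SAP does not support reading this as a failure of the secondary safety endpoint, which is adverse events and is already baseline-referenced and graded. The primary analysis is not affected. It is a worthwhile, inexpensive improvement.

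**What to change.** In Section 10.3, replace or supplement the below/above percentages with descriptive tables by arm, for each hematology and chemistry parameter:

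- Shift from baseline to each scheduled visit and to the worst post-baseline value, separately in the low and high directions, including unscheduled samples. Use CTCAE grade where a numeric grade is defined and low/normal/high otherwise.
- Number and percentage of patients with a treatment-emergent abnormality, defined as out of range or graded after the first dose when normal at baseline, or a higher grade than at baseline.
- Number and percentage of patients with grade 3 or higher.

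State the denominator for each table and keep the section free of testing, as now. The change should be made before unblinding. It needs SAP wording and a few more programmed tables from data already collected, with no new samples or visits. The drawbacks are a longer table set and the absence of a CTCAE grade for some parameters.
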